feeding for individuals with upper extremity impairments—a key activity of daily living that contributes to personal dignity, autonomy, and quality of life.

The claims for clinical performance and effectiveness to be verified in this study include:

- The device can be safely and effectively operated by the intended users (patients and caregivers) in a home, school, or community setting.
- The device is recommended and integrated into practice by clinical professionals who support individuals with feeding-related disabilities.
- The design features, controls, and user interface support efficient, effective, and satisfactory use.
- The device enables users to independently complete a minimum of five meals during a one-week trial period without undue burden on caregivers or providers.

This clinical investigation also aims to verify that supporting materials (e.g., Quick Start Guide, Instructions for Use, and MDNA form) are usable and that the overall user experience aligns with expectations for performance, ease of use, and satisfaction. These claims will be evaluated through mixed-methods data collection, including surveys and semi-structured interviews. No safety claims are being assessed in this study. Obi Gen 3 is a Class I medical device with minimal risk and has undergone benefit-risk analysis and mitigation per ISO 14971. However, participants will be monitored for device-related issues or unanticipated problems during the trial.

b) Objectives, primary and secondary, are described as ‘superiority,’ ‘non-inferiority,’ or ‘equivalence,’ if applicable.

PRIMARY: Validate whether the production equivalent enhanced Obi3 device design conforms to the formally defined user needs and intended use (per IFD-DES-054-1, Obi Validation Plan, Gen3)

SECONDARY:

- Determine patient usability in accordance with the Matching Person & Technology Assistive Technology Framework.
- Determine caregiver usability in accordance with questions from the Caregiver Burden Index.
- Determine provider perspectives following the SUS as a standardized outcome measure.
- Obtain provider feedback regarding the efficacy, efficiency, and satisfaction of the Obi clinical assessment forms and the associated process.
- Obtain other qualitative feedback regarding the perceived strengths and weaknesses of the Obi design.

c) Scientific justification and clinical relevance for effect sizes, non-inferiority margins, or equivalence limits, where applicable.

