This clinical investigation is a non-randomized, non-comparative usability study designed to evaluate whether the Obi Gen 3 Medical Robotic Feeding Device conforms to its intended use and meets documented user needs. The purpose of the study is not to assess therapeutic effectiveness or to compare outcomes across intervention groups but to validate device usability and stakeholder satisfaction across real-world settings.

Given the nature and objectives of the study, randomization, blinding, and allocation concealment are not applicable. However, several measures will be taken to minimize or avoid bias and manage potential confounding factors:

1. Standardized Protocols and Training

All participants (providers, caregivers, and patients) will engage with the device under a standardized study protocol, including consistent onboarding materials, instructional documents, and usage expectations (e.g., a minimum of five meals during the trial period). These materials were developed based on prior formative feedback and are provided in uniform formats to reduce variability in participant experience.

2. Structured Data Collection Tools

Usability feedback will be collected using validated instruments (e.g., System Usability Scale, Matching Person & Technology framework) and semi-structured interview guides. These tools ensure consistency in gathering information, reduce interviewer bias and facilitate comparisons across stakeholder groups.

3. Triangulation of Stakeholder Perspectives

The study design allows for triangulation of findings by including data from three distinct stakeholder groups (providers, caregivers, and patients). This multi-perspective approach reduces the risk of single-source bias and provides a broader understanding of device usability in real-world contexts.

4. Post-Use Feedback After Trial Exposure

Participants provide their usability ratings and feedback only after completing the one-week trial. This approach helps minimize expectation bias and ensures responses reflect the user experience with the device.

5. Blinding of Data Analysts (if applicable)

The Principal Investigator will conduct the data analysis but will not be involved directly in participant recruitment or data collection, reducing the potential for confirmation bias during the interpretation of results.

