Collectively, these measures are designed to support the credibility, reproducibility, and transparency of findings from this usability-focused clinical investigation.

c) Primary and secondary endpoints, with rationale for their selection and measurement. If applicable, composite endpoints, with rationale for their selection and measurement.

Primary Endpoint

The primary endpoint of this clinical investigation is to determine whether the production equivalent Obi Gen 3 device fulfills its intended use and formally defined user needs across three key stakeholder groups: patients, caregivers, and providers. This endpoint reflects the device's design validation objective under FDA and ISO guidelines for Class I medical devices.

To assess this endpoint, the study uses a mixed-methods approach that includes:

- Usability survey responses gathered post-trial via Qualtrics,
- Qualitative interview data to capture real-world experiences and
- Evidence of independent feeding success (i.e., completion of a minimum of five meals during the one-week trial period for patient participants).

Rationale: This endpoint aligns with ISO 13485 and FDA QSR requirements for verifying that a device conforms to documented design inputs and intended use in its target environment. Given that the device facilitates daily living activities rather than delivers clinical treatment, usability, and stakeholder satisfaction are the most relevant performance indicators.

Secondary Endpoints

Secondary endpoints are designed to provide a multi-dimensional understanding of the user experience and support future design refinement and stakeholder-specific training materials.

These include:

1. **Patient Usability** will be measured using an adapted version of the Matching Person & Technology (MPT) Framework and adult and pediatric versions. The study focuses on compatibility between the user and device, perceived benefits, and likelihood of long-term adoption.
2. **Caregiver Usability** will be measured using the System Usability Scale (SUS) and the Matching Person & Technology (MPT) Framework, an adult version adapted for the context of this study. Additionally, a few selective questions from the Caregiver Burden index will help to describe this stakeholder group to understand better the impact of Obi-Gen 3 use on time demands, emotional strain, and caregiving workload.

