Because Obi Gen 3 is a non-implantable, non-therapeutic, electromechanical device with no internal measurement sensors requiring calibration, no additional calibration procedures are required during the investigation. In the rare event of a device malfunction or performance concern, participants will be instructed to notify the study coordinator immediately, and the sponsor will either replace the device or conduct further investigation as appropriate.

In addition to the device, the following tools will be used for assessing clinical investigation variables:

- Obi Gen 3 Assessment Forms (D-FRM-021, Obi MDNA) (developed by the sponsor for clinical assessment and workflow documentation)
- Data Collection Tools including:
 - **Qualtrics** – a secure, HIPAA-compliant online platform used to distribute and collect all electronic surveys, rating scales, and interview responses
 - **System Usability Scale (SUS)**
 - **Matching Person & Technology Framework** – adapted
 - **Caregiver Burden Index** – selected items relevant to feeding support

All electronic data collection tools (i.e., Qualtrics) are maintained by the vendor and subject to routine system monitoring, encryption, and security updates per HIPAA and institutional data security policies.

f) Any procedures for the replacement of subjects (generally, not applicable to randomized clinical investigations).

This usability study includes patients, caregivers, and providers as stakeholders and does not involve treatment allocation or randomization.

As such, formal subject replacement procedures are not applicable. Participants may withdraw from the study at any time without penalty, and no individual will be replaced on a one-to-one basis; however, if attrition occurs early in the study (e.g. before completion of the minimum trial period or primary usability data are collected), the sponsor and study team may continue recruitment to maintain a robust and diverse sample that reflects the target user population.

All data from participants who withdraw will be handled according to data management protocols, and partial data may be included in the analysis when appropriate and ethically permissible. Efforts will be

made to ensure adequate enrollment within each stakeholder group (providers, caregivers, and patients) to meet the target sample size and fulfill the study's objectives.

g) Investigation sites: number, location, and, if appropriate, differences in investigation site environment.

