Subjects may be withdrawn from the clinical investigation at any time due to voluntary withdrawal, investigator decision, or other unforeseen circumstances. Regardless of cause, all early terminations must be documented clearly in the Case Report Form (CRF) (attached to this protocol), including the specific reason for withdrawal. The following outlines the criteria and procedures for subject withdrawal:

Early Termination – General Considerations: All early exits from the study will be promptly recorded, and the rationale for withdrawal should be documented in the CRF to ensure traceability, transparency, and compliance with study oversight requirements.

Failure During Initial Use - While inclusion/exclusion criteria with pre-screening and in-office assessment that is part of the standard operating procedure will optimize appropriate participant selection, they may not be 100% predictive of device compatibility. In some instances, a subject may meet pre-screening criteria but be unable to use the Obi Gen 3 device safely or effectively during initial use. These cases will be identified early—typically on the first day of the trial—and such individuals will be withdrawn from the study. These withdrawals must be clearly documented in the CRF and the reason and relevant observational notes.

Voluntary Withdrawal of Consent - Subjects (or their legal representatives) have the right to withdraw consent and discontinue participation in the study at any time and for any reason, without penalty or loss of benefits. If informed consent is withdrawn, no additional data will be collected from the subject beyond the point of withdrawal. All data previously collected up to the point of withdrawal may be retained and used for analysis unless the subject explicitly requests full data removal, as outlined in the consent form.

Investigator-Initiated Withdrawal - If, at any time during the investigation, the Principal Investigator determines that continued participation poses an unforeseen risk to the subject's well-being or safety—or for other clinical, behavioral, or protocol-related reasons—the subject may be withdrawn from the study. The justification for investigator-initiated withdrawal must be documented in the CRF, and the subject (or caregiver) must be informed of the decision following ethical and regulatory standards.

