Devices used in during the study will be returned to DESIN LLC, visually inspected, functionally evaluated, cleaned, disinfected and otherwise reconditioned as needed in accordance with DESIN LLC's SOP120. These devices will then be approved to enter the company's trial device fleet. These devices will be used with new prospective customers.

A.6.5 Monitoring Plan

General outline of the monitoring plan to be followed, including access to source data and the extent of source data verification planned.

There is no official monitoring plan developed. However, to ensure adequate monitoring of the study, the principal investigator and/or study team shall cooperate with DESIN LLC. This includes, but is not limited to, allowing the assessment of facilities utilized for this study, providing access to subject report forms, and subject medical records reasonably requested.

A.7. Statistical Design and Analysis

With reference to A.5 and A.6, the description of and justification for statistical design and analysis of the clinical investigation shall cover the following.

a) Analysis population (e.g. intention-to-treat, per-protocol, as-treated) and procedures that take into account all the data.

This clinical investigation is a non-randomized, non-comparative, mixed-methods usability study intended to evaluate whether the production equivalent Obi Gen 3 robotic feeding device meets the documented user needs and intended use across stakeholder groups. As such, the primary focus of the statistical design is on descriptive and qualitative analysis rather than hypothesis testing or inferential statistics.

All participants who complete informed consent and the survey be included in the analysis population. Given the non-interventional nature of the study, the analysis will follow an as-treated approach, with all available data from each stakeholder group included in the final analysis. Participants who after consent but before completing any trial procedures will be excluded from the analysis population. Missing data will be documented but not imputed, as the primary intent is to assess observed usability and feedback trends.

b) Descriptive statistics of baseline data, treatments, safety data and where applicable, primary and secondary endpoints.

Descriptive statistics will be used to summarize:

- Baseline demographic and clinical characteristics, including age, gender, diagnosis, and prior experience with assistive technology.

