Given the short duration and minimal risk nature of this usability study, the expected drop-out rate is anticipated to be low (less than 10%). Participants will be engaged for a one-week home or community-based trial of the Obi Gen 3 device,. The limited time commitment, non-invasive nature of participation, and flexibility of remote data collection (via Qualtrics and telephone interviews) are expected to support high retention.

Potential reasons for early withdrawal or loss to follow-up may include:

- Lack of interest or time to complete the trial period or follow-up activities
- Health-related issues or changes in caregiving responsibilities
- Technological issues or accessibility barriers (e.g., inability to access electronic surveys)
- In rare cases, discomfort or dissatisfaction with the device

Because the study does not involve treatment, diagnostic procedures, or invasive interventions, death is not anticipated and is not an endpoint. Any withdrawal or loss to follow-up will be documented with reason, when available. Data collected prior to withdrawal will be included in the analysis, consistent with an as-treated approach.

f) The rationale for the number of procedures to be performed by a single user as part of the learning curve and how these data are to be analysed, if applicable.

Given that this investigation evaluates the usability of a robotic feeding device designed for individuals with upper extremity impairments, caregivers, and providers, it is important to account for the initial learning period associated with device setup, operation, and integration into daily routines. The one-week trial period with a minimum expectation of five completed meals per patient/caregiver dyad is designed to reflect a realistic and sufficient exposure to allow users to become familiar with the device and overcome early learning curve effects.

This threshold was selected based on preliminary feedback from internal evaluations and stakeholder consultations, which indicated that users typically require **3–5 sessions**, to feel comfortable with basic functions (e.g., powering on, positioning the spoon, switching food compartments). For providers, the requirement to recommend and assess at least one patient supports evaluation of the device within their existing workflow, allowing observation of setup, training, and follow-up in a practical setting.

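### Patients withdrawn because they cannot use Obi3 at first use give no rating, and the protocol does not settle whether they count in the five-meal result

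*Protocol*

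**What the plan says.** **Withdrawal.** Protocol A.6.3 c) i) concerns subjects who met the screening criteria but prove "unable to use the Obi Gen 3 device safely or effectively during initial use". It continues: "These cases will be identified early—typically on the first day of the trial—and such individuals will be withdrawn from the study". Reason and notes go in the CRF. Under A.6.3 d) enrolment follows consent and the in-office assessment, so these are enrolled subjects and not screen failures.

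**Ratings.** A.6.1 b) says: "Participants provide their usability ratings and feedback only after completing the one-week trial". In A.6.1 c) the training-material endpoint rests on post-trial feedback.

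**The five-meal measure.** A.6.1 c) lists among the evidence for the primary endpoint: "Evidence of independent feeding success (i.e., completion of a minimum of five meals during the one-week trial period for patient participants". A.5 a) makes it a claim to be verified: "The device enables users to independently complete a minimum of five meals during a one-week trial period".

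**Who is analysed.** A.7 a) states: "All participants who complete informed consent and the survey be included in the analysis population". The same paragraph then adopts an as-treated approach using all the data at hand, and excludes only those who leave before any trial procedure. A.7 e) 6) adds: "Data collected prior to withdrawal will be included in the analysis, consistent with an as-treated approach". A.6.3 c) ii) and A.7 m) also retain partial data.

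**Further recruitment.** For early attrition, A.6.1 f) gives this condition: "before completion of the minimum trial period or primary usability data are collected), the sponsor and study team may continue recruitment". A.6.3 c) iii) is narrower.

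**Sensitivity analysis.** A.7 n) declares it not applicable.

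**The concern.** A patient who cannot use the device at first use cannot complete five meals with it, and so counts against the claim in A.5 a). That inability is also what removes the patient from the study. If the patient then falls outside the denominator, the reported rate describes only people for whom the device already worked at first use.

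The same patients are missing from the patient ratings of usability and from the patient feedback on the Quick Start Guide and Instructions for Use, where their experience would be most informative. A.5 d) places the value of the study in finding what helps and hinders use, so losing these patients costs more here than their number suggests.

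Describing drop-outs separately, as A.7 m) plans, is useful but does not change the success rate itself.

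**Working it through.** **Step 1. Trace one such patient through the rules.**

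| Rule | Section | Patient withdrawn on day 1 |
|---|---|---|
| Enrolled after consent and in-office assessment | A.6.3 d) | In the study |
| Ratings only after the completed week | A.6.1 b) | No rating |
| Consent plus survey | A.7 a), opening rule | Outside the analysis population |
| Excluded only if no trial procedure was completed | A.7 a), later in the paragraph | Not excluded, having begun the home trial |
| Data before withdrawal retained | A.6.3 c) ii), A.7 e) 6), A.7 m) | Inside, with fewer than five meals |

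The patient is out of the five-meal denominator under one rule and in it, as not achieved, under the others. No section says which rule applies to this measure.

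**Step 2. Direction.** Let *s* be the patients completing five meals, *c* those who stay in, and *k* those withdrawn at first use.

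- Completer rate = s / c
- Starter rate = s / (c + k)

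Since k ≥ 0, the completer rate is never the lower of the two.

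**Step 3. Inputs.** A.6.3 h) gives 20 patients (5 adults + 15 children = 20) and 60 participants in all (20 + 20 + 20 = 60, which reproduces the stated total). A.7 e) 6) expects drop-out below 10%. The number of first-use failures is not given. I assume that the drop-out figure applies to the patient group and consists entirely of such failures.

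**Step 4. No top-up.** k/20 < 0.10 allows k = 0 or 1.

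- k = 0: no difference.
- k = 1, all others succeed: 19/19 = 100% against 19/20 = 95.0%, a gap of 5.0 points.
- k = 1, two who stay also miss five meals: 17/19 = 89.5% against 17/20 = 85.0%, a gap of 4.5 points.

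**Step 5. Recruitment continued until 20 stay in.** k/(20 + k) < 0.10 allows k up to 2, since 2/22 = 9.1% and 3/23 = 13.0%. If all who stay succeed:

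- k = 1: 20/20 = 100% against 20/21 = 95.2%, a gap of 4.8 points.
- k = 2: 20/20 = 100% against 20/22 = 90.9%, a gap of 9.1 points.

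**Step 6. Age groups listed in A.7 l), one failure, no top-up, all others succeed.**

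- Adults: 4/4 = 100% against 4/5 = 80.0%.
- Children: 14/14 = 100% against 14/15 = 93.3%.

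The adult gap is a single person in five and should be read as such.

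**The case against.** The strongest reply is that little is lost and nothing is decided by it. The withdrawal reason is in the CRF, the number of meals completed is summarised (A.7 b)), and the drop-out rate and pattern go in the final report (A.7 m)). A reader could work out 19/20 unaided. A.7 a), read as a whole, leans towards keeping available data, so the conflict comes down to one loose sentence. These patients may also be seen as a compatibility problem that screening missed and not as a failure of the design, and rating a week of use after that week is a deliberate choice.

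Much of this stands, and it limits the point. Several stronger readings are tempting and are not supported:

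- **That the protocol states two denominators for the five-meal measure.** It states none. The conflict is between its general population rules.
- **That this is the only defined patient measure.** A.7 g) also defines a drop in the ICF qualifier for functional eating, with its own threshold of 85% and an explicit one-week-completer denominator.
- **That the pass/fail result is at risk.** Five-meal completion is not among the A.7 g) criteria and has no threshold.
- **That withdrawn patients will be replaced.** A.6.1 f) is permissive and rules out one-to-one replacement. The examples in A.6.3 c) iii) concern subjects who leave before the trial or the in-office assessment.
- **That all usability evidence is selected.** Caregivers and providers linked to a withdrawn patient may still respond.
- **That patients who are merely still learning will be withdrawn.** The text does not say so.

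What the reply does not answer is that the rate itself is left open, on a measure offered as primary-endpoint evidence, when the choice can move it in only one direction.

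**Conclusion.** The point holds as a limited one. Patients withdrawn at first use give no patient rating, and the general rules disagree on whether they count in the five-meal result. Under the survey-completer rule the rate can only lean favourable.

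The size cannot be known from the protocol. On the assumption that all drop-out is first-use failure and stays below 10%, the gap without top-up is zero or about 5 points. It reaches 9.1 points only with two failures and continued recruitment, which the protocol allows but does not require. A.7 e) 6) does not list inability to use the device among its reasons for drop-out, so the true number may lie outside this range in either direction.

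What is affected is the reported evidence for the primary endpoint and the performance claim in A.5 a), not the formal pass/fail thresholds. Because the data are already collected and the correction costs almost nothing, it is worth making.

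**What to change.** Keep the withdrawal rule as it stands, including immediate withdrawal for unsafe use.

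1. In A.7 a), state that the five-meal measure is reported among all enrolled patients who started the home trial, that withdrawals at first use count as not achieved, and that the completer figure is shown beside it.
2. State that any additional recruits are added to this denominator and do not take the place of withdrawn patients.
3. In the CRF, code the first-use withdrawal reason as unsafe or not effective.
4. Report how many patients gave no rating, next to the usability and training-material results.

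Optional: send the Quick Start Guide and Instructions for Use items to patients withdrawn at first use who still consent.

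The cost is a few sentences, one CRF code and one table row, plus a short Qualtrics branch if the optional step is taken. The downside is that the reported rate may be slightly less favourable.

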Given the minimal-risk nature of the study, no intensive or intrusive tracking methods (e.g., home visits) will be used. Participants will be informed during the consent process that follow-up is optional and that they may discontinue participation at any time without consequence.

iii.) whether and how subjects are to be replaced.

Given the nature of this usability study and the relatively small, targeted sample size, subjects who withdraw voluntarily or are lost to follow-up during the study period will not be replaced. However, if a subject withdraws before completing any meaningful portion of the data collection (e.g., before starting the Obi Gen 3 trial period or before completing in-office assessments), the study team may recruit an additional participant to maintain representation across stakeholder groups (providers, caregivers, and patients). Replacement will occur only as needed to ensure data completeness or demographic diversity aligned with the study's exploratory objectives.

d) Point of enrollment.

Participants are considered enrolled in the study after providing informed consent (or assent, where applicable) and after completing an initial in-office clinical assessment by a qualified provider (typically an occupational therapist) as outlined in SOP220. This point marks the subject's formal inclusion in the study and the beginning of data collection activities using the HIPAA-compliant Qualtrics platform.

e) Point of randomization, if applicable. Randomization does not apply to this investigation.

f) Total expected duration of the clinical investigation.

The total expected duration of this clinical investigation is approximately three (3) months, spanning from April 2025 through June 2025. This time frame includes:

- Pre-screening, recruitment, and enrollment of participants across all stakeholder groups (providers, caregivers, and patients),
- Completion of a one-week home/community trial of the Obi Gen 3 device by up to 60 participants,
- Post-trial survey and interview data collection,
- Final data analysis and reporting of usability outcomes.

The duration also accommodates staggered enrollment and rolling recruitment, which will occur on a first-come, first-served basis until target sample sizes are reached. The study timeline may be adjusted slightly based on participant availability and operational needs but is not expected to exceed the nine-month window.

g) Expected duration of each subject's participation.

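### The two replacement rules conflict for patients who leave after starting the home trial, and the completer-only 85% criterion drops those who could not use the device under either rule

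*Protocol*

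**What the plan says.** Four places in the protocol bear on this point.

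- **A.6.1 f)** says that "no individual will be replaced on a one-to-one basis". A looser provision follows for subjects lost early: "if attrition occurs early in the study (e.g. before completion of the minimum trial period or primary usability data are collected". For that case the section allows more enrolment, in these words: "the sponsor and study team may continue recruitment to maintain a robust and diverse sample". The trigger covers people who are already using the device at home. The section also refers to meeting the target sample size.
- **A.6.3 c) iii)** says that "subjects who withdraw voluntarily or are lost to follow-up during the study period will not be replaced". The exception applies "if a subject withdraws before completing any meaningful portion of the data collection (e.g., before starting the Obi Gen 3 trial period"; an unfinished in-office assessment is its other example. It closes with a purpose clause: "Replacement will occur only as needed to ensure data completeness or demographic diversity".
- **A.6.3 c) i), Failure During Initial Use**, covers patients who pass screening but prove unable to use the device safely or effectively, typically on day one: "such individuals will be withdrawn from the study".
- **A.7 g)** sets the pass criteria on subjects who finish the one-week trial. The functional-eating performance qualifier must improve by at least one grade in 85% of patients, and half of respondents must judge each user need fulfilled.

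A.6.3 h) sets the patient target at 20. A.7 e) 6) expects drop-out below 10%.

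**The concern.** Inability to use the device is one of the outcomes that a usability validation exists to detect. The plan withdraws such patients, leaves them out of the percentage that decides pass or fail, and does not settle whether new patients may be recruited in their place. Two teams following this protocol could handle the same patient differently, and a favourable completer percentage could be reported although several starters could not use the device at all.

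**Working it through.** **1. The replacement rules side by side**

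| Patient | A.6.1 f) | A.6.3 c) iii) |
|---|---|---|
| Leaves before starting the home trial | further recruitment allowed | further recruitment allowed |
| Starts, then withdraws voluntarily or is lost before the minimum use is reached | further recruitment allowed | not replaced |
| Starts and is withdrawn as unable to use the device | further recruitment allowed | not clearly covered: the bar names only voluntary withdrawal and loss to follow-up |

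The second row is a contradiction. The third is a gap in A.6.3 c) iii).

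**2. The plan's own numbers**

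20 + 20 + 20 = 60 reproduces the stated total. The cited minimum is 15 per user population. Allowing for 10% loss, 15 / 0.90 = 16.7, so 17. With 20 patients, 20 × 0.90 = 18 remain. If patients are taken as one user population, 20 covers the cited minimum without adding recruits.

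**3. Effect of the denominator, and of adding recruits**

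I read 85% as at least 85%, so n completers need ceil(0.85 × n) successes. Let k of the first 20 starters leave. The protocol gives no k, so it is varied. With top-up, k new patients are assumed to start and all to complete. Results that just pass:

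| k | No top-up: completers | No top-up: starters | Top-up: completers | Top-up: starters |
|---|---|---|---|---|
| 1 | 17/19 = 89.5% | 17/20 = 85.0% | 17/20 = 85.0% | 17/21 = 81.0% |
| 2 | 16/18 = 88.9% | 16/20 = 80.0% | 17/20 = 85.0% | 17/22 = 77.3% |
| 4 | 14/16 = 87.5% | 14/20 = 70.0% | 17/20 = 85.0% | 17/24 = 70.8% |

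At k = 4 the gap between completers and starters is 17.5 points without top-up and 14.2 points with it. The gap therefore comes from the denominator, not from replacement.

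**4. Expected rates**

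Let p be the true success rate among completers. It is not in the protocol and is assumed equal for added recruits. The expected completer rate is p with or without top-up. Over all starters, with leavers counted as not improved, it is (20 − k)p/20 without top-up and 20p/(20 + k) with it. At p = 0.90 and k = 4 these are 0.72 and 0.75, against 0.90 among completers.

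**5. Chance of meeting 85%**

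P(X ≥ ceil(0.85n)) with X binomial(n, p):

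| | p = 0.80 | p = 0.85 | p = 0.90 | p = 0.95 |
|---|---|---|---|---|
| k = 1, no top-up (17 of 19) | 0.237 | 0.441 | 0.705 | 0.933 |
| k = 2, no top-up (16 of 18) | 0.271 | 0.480 | 0.734 | 0.942 |
| k = 4, no top-up (14 of 16) | 0.352 | 0.561 | 0.789 | 0.957 |
| Topped up to 20 (17 of 20) | 0.411 | 0.648 | 0.867 | 0.984 |

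The rise occurs because 17/20 is exactly 85%, while 16 to 19 completers must exceed it.

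**The case against.** A reader might infer that the looser rule inflates the pass rate by exchanging failures for new patients until 20 completers exist. The documents do not support that. A.6.1 f) rules out one-to-one replacement and only permits further recruitment, the target in A.6.3 h) counts people recruited rather than completers, and no section guarantees 20 completers. Nothing suggests that later recruits would be better candidates: they pass the same SOP220 screening and enrolment is first-come, first-served. The expected completer rate is unchanged, and the denominator problem exists with no replacement at all.

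Three further points carry weight.

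- Losses are not hidden. Exits and reasons go in the case report form, and A.7 m) requires the rate and pattern of drop-out to be described in the final report. That does not alter the pass/fail percentage.
- Four failures among 20 is 20%, above the expected drop-out of under 10%. With one leaver and no top-up, a just-passing result is still 85.0% of starters. However, the drop-out reasons listed in A.7 e) 6) do not name inability to use the device, so that expectation may not include first-use failures.
- Counting every leaver as a failure is debatable, since A.6.3 c) ii) foresees unrelated reasons such as competing demands, and the plan does not impute missing data. This stands for unrelated leavers. It does not stand for first-use failures, whose inability to use the device has been observed.

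**Conclusion.** The conflict between A.6.1 f) and A.6.3 c) iii) is real for subjects who start the home trial and then leave voluntarily or are lost. For first-use failures, A.6.1 f) applies and A.6.3 c) iii) is unclear. Separately, A.7 g) removes first-use failures from the 85% decision under either rule and so overstates success: 87.5% against 70.0% in the illustration with four failures among 20. It also sits badly with the as-treated use of all available data described in A.7 a) and A.7 e) 6).

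Top-up is a secondary matter. It makes the loss less visible in the completer count and raises the chance of meeting 85% by rounding. Over p = 0.80 to 0.90 the rise is about 13 to 17 points with two leavers and 6 to 9 points with four. These sizes rest on assumed values of k and p, and on added recruits who all complete with the same p.

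**What to change.** 1. **One replacement rule.** Use the same text in A.6.1 f) and A.6.3 c) iii): further recruitment only for a subject who never started the home trial. State explicitly that patients withdrawn for failure at initial use have started and fall under this rule.
2. **Denominator in A.7 g).** Keep patients withdrawn for inability to use the device in the 85% denominator, counted as not improved. This concerns counting only and leaves the withdrawal decision untouched.
3. **Sensitivity analysis.** Pre-specify the result over all starters, with other leavers counted as not improved, beside the primary result. A.7 n), which now declares sensitivity analysis not applicable, needs a matching edit.
4. **Reporting.** Give the numbers of starters, leavers by reason, and added recruits.

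The cost is protocol wording, a somewhat less favourable pass rate and possibly slightly fewer completers. At the expected drop-out, 20 starters leave at least 18 completers, and even four losses leave 16, against the cited minimum of 15 if patients are taken as one user population.
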